### Outcomes:

The primary outcome will be:

- 1) **72-hour hospital survival**, defined as patient status (alive/dead) at 72 hours after the initial onset of cardiac arrest.

Secondary outcomes will include:

- 1) **Return of Spontaneous Circulation (ROSC)**, defined as the presence of palpable pulses upon ED arrival.
- 2) **Airway Management Clinical Course**, including sequence of ETI/LT insertion, ETI/LT insertion success and time, number of ETI/LT insertion attempts, and airway conversion (change of LT-to-ETI, or ETI-to-LT) in the receiving Emergency Department.
- 3) **Adverse Events**, including initially unrecognized airway misplacement (including endotracheal tube misplacement), inadequate ventilation requiring airway exchange, vomiting, oropharyngeal, hypopharyngeal or gastrointestinal trauma, and pneumothorax.
- 4) **Hospital Survival**, defined as patient status (alive/dead) at hospital discharge.

- 5) **Hospital Survival with Good Neurologic Function**, defined as Modified Rankin Score  $\leq 3$  upon hospital discharge.

**Analysis:** We will calculate the difference in outcomes divided by the estimated “robust” standard error based on the Huber-White sandwich estimator in order to account for within cluster correlation and variability, which might depart from the classical assumptions. To quantify the treatment effect, we will calculate the 95% CI for the difference in event rates. We will perform the analysis on an intention-to-treat (primary analysis) as well as treatment-received bases (secondary analysis).

**Sample Size:** The trial will require 2,612 subjects (1,306 per group) to have 85% power to detect a 4.5% absolute difference in 72-hour survival, given baseline survival of 13.7% and an overall two-sided alpha of 0.05. To allow for subject withdrawal and lost-to-follow-up, the trial will enroll up to 3,000 subjects.

**Regulatory and Ethical Considerations:** The trial will be carried out under federal rules for Exception from Informed Consent (EFIC) outlined by the guidance document “Waiver of Informed Consent Requirements in Certain Emergency Research” (Federal Register, Vol. 61, pp. 51531-51533, November 1, 1996 - <http://www.gpo.gov/fdsys/pkg/FR-1996-10-02/html/96-24968.htm>), OHRP “Basic HHS Policy for Protection of Human Research Subjects” (45 CFR 46.101(i) - <http://www.hhs.gov/ohrp/humansubjects/guidance/45cfr46.html#46.101>), and FDA regulations 21 CFR 50.24.

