### 13. Random Allocation and Blinding

#### 13.1 Random Allocation Method

The airway intervention will be cluster randomized at the EMS agency level with periodic crossover. Each site will be subdivided into multiple clusters by EMS agency, station, or other unit as appropriate to the site’s EMS structure. Each cluster will be scheduled to crossover to the opposite treatment – typically once or twice per year during the trial. The use of crossovers is efficient and minimizes unbalanced treatment assignment.

If more than one participating EMS agency is present on scene, the first arriving unit will determine the study treatment assignment. If a non-ROC EMS agency arrives first on scene, the subsequent first arriving ROC EMS agency will perform airway management as randomized.

The randomization of clusters will be stratified by site. Within each site, clusters will be organized into relatively homogeneous groups with respect to the number of patients expected to be treated over the course of the study in that cluster. All clusters will crossover between intervention assignments at least once (i.e., have at least two distinct treatment periods). If necessary, some clusters with high episode rates will crossover more than once.

Random assignment of treatment sequence will be performed by the coordinating center prior to the start of the study.

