### 15.3 Primary Analysis – 72-Hour Survival

The primary hypothesis is that there is no difference in OHCA 72-hour survival between primary LT- and primary-ETI airway management strategies. The primary outcome of interest is 72-hour survival. We will calculate the difference in outcomes divided by the estimated “robust” standard error based on the Huber-White sandwich estimator in order to account for within cluster correlation and variability, which might depart from the classical assumptions. To quantify the treatment effect, we will calculate the 95% CI for the difference in event rates. Since

[figure not shown]

Figure 12 - Anticipated CONSORT Diagram

randomization includes all eligible OHCA patients, we will not stratify the primary analysis by initial cardiac rhythm. We will perform the analysis on intention-to-treat (primary) as well as as-treated (secondary) bases.

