## **15.5 Subgroup Analyses**

OHCA outcomes are known to vary for different patient subsets. For example, OHCA survival is approximately 28.4% for patients with an initial “shockable” cardiac rhythms (ventricular fibrillation or tachycardia) and 6.2% for non-shockable rhythms (pulseless electrical activity and asystole). We will explore multiplicative associations between airway management strategy (ETI vs. LT) and the pertinent subgroups, including:

- Initial cardiac rhythm (shockable vs. non-shockable);
- Bystander witnessed arrest (yes vs. no);
- EMS response time (911 call to arrival on-scene: <10 vs. ≥10 mins);
- BLS unit capability of performing LT insertion (yes vs. no);
- Time of airway placement after rescuer arrival on-scene (early [<10 minutes] vs. later [≥10 minutes]);
- Use of NMB (RSI) before or during airway insertion efforts (yes vs no);
- Age (<65 vs. ≥65 years).
- Placement of advanced airway after ROSC.
- Initial airway management with non-rebreather mask only (passive ventilation).

Initial airway management with video laryngoscopy. If an [airway x subgroup] interaction is statistically significant, we will stratify the analysis by the subgroup.

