**Table 4 - Sample Size Estimates**  
Effect sizes based upon 13.7% baseline 72-hour survival.

in 72-hour survival after OHCA, with an overall significance level (adjusted for interim analyses) of 0.05 and accommodating up to a 5% loss of precision due to cluster randomization (with crossover).

The estimated effect sizes are based upon observations from the ROC PRIMED Trial. In ROC PRIMED, baseline 72-hour survival was 13.7%. There was a 5.0% absolute difference in 72-hour survival between ETI (13.7%) and SGA (8.7%). To account for potential confounders, for this trial we will use a more conservative figure of 4.5% to represent a minimal clinically significant difference. We designed the trial to have 85% power to detect this difference. Therefore, the required minimum sample size is 2,612 subjects (1,306 per group). To allow for subject withdrawal and loss to follow-up, we have budgeted to enroll up to a total of 3,000 subjects.

The participating US ROC sites (Alabama, Dallas, Milwaukee, Pittsburgh, Portland and San Diego) historically treated over 3,000 OHCA requiring advanced airway management in 2013. Therefore, we expect to have adequate capacity to enroll the requisite number of subjects over the anticipated three-year study period.

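### The primary analysis is a valid unadjusted risk difference, but it leaves out initial rhythm and the site and period structure of the design; adjusting for rhythm alone could cut its variance by roughly 6% to 9%.

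*Combined protocol and SAP*

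**What the plan says.** Section 15.3 (and the Analysis paragraph of section 3) divides the between-arm difference in 72-hour survival by a Huber-White standard error, which is there to allow for correlation within clusters, and reports a 95% confidence interval for the difference. No covariate is named. On rhythm, the section says that because "randomization includes all eligible OHCA patients, we will not stratify the primary analysis by initial cardiac rhythm".

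The design has more structure than this. Section 13.1 states: "The randomization of clusters will be stratified by site". Clusters are grouped within site by expected volume, and every cluster crosses over at least once, some more often.

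Rhythm enters only in section 15.5, as one of several subgroup interactions. That section reports that "OHCA survival is approximately 28.4% for patients with an initial" shockable rhythm, against 6.2% for non-shockable rhythms. It gives neither the time point of these rates nor the share of patients with a shockable rhythm.

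**The concern.** The reason given for not stratifying by rhythm explains why all rhythms belong in the estimand. It is not a reason to leave rhythm out of the estimator, since a rhythm-adjusted or rhythm-standardised risk difference targets the same all-patient effect. By the protocol's own figures rhythm is a strong predictor of survival, and the data are already needed for section 15.5.

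Two things are at stake. The first is precision: part of the spread of the crude difference comes from chance differences between arms in the rhythm mix. The second is protection. Agencies may be suspended, readmitted or removed (sections 17 and 22.1, Appendix 3), and a period can be cut short. A cluster lost partway through its sequence then contributes unequally to the two arms. The crude difference would carry the resulting site and calendar differences into the point estimate, and a robust standard error does not re-centre an estimate.

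**Working it through.** **1. The plan's sample size.** Section 3 gives the design as "given baseline survival of 13.7% and an overall two-sided alpha of 0.05". Section 16.1 adds "we will use a more conservative figure of 4.5% to represent a minimal clinically significant difference" and "We designed the trial to have 85% power to detect this difference", with up to 5% loss of precision for clustering. Take 13.7% against 18.2%, unpooled variance, and the 5% as an inflation of the standard error (variance × 1.05² = 1.1025):

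- Sum of arm variances: 0.137 × 0.863 + 0.182 × 0.818 = 0.1182 + 0.1489 = 0.2671
- n per arm = 1.1025 × 0.2671 × (1.960 + 1.036)² / 0.045² = 1,306 after rounding up, so N = 2,612

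This is the stated figure exactly. It comes from an unadjusted comparison. The standard error at this size is √(1.1025 × 0.2671 / 1,306) = 0.01502, and power is Φ(0.045/0.01502 − 1.960) = 85.0%.

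**2. Variance explained by rhythm.** Let s be the shockable share and p = 0.284s + 0.062(1 − s). Then

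R² = s(1 − s)(0.284 − 0.062)² / [p(1 − p)].

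The share is not stated. Reading the two rates as 72-hour survival and solving for 13.7% overall gives s = (13.7 − 6.2)/(28.4 − 6.2) = 33.8%. Then R² = 0.338 × 0.662 × 0.222² / (0.137 × 0.863) = 9.3%.

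**3. What this buys at s = 33.8%.**

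- Variance × (1 − 0.093), so the standard error falls by 1 − √0.907 = 4.8%, to 0.0143
- Power at 2,612: Φ(0.045/0.0143 − 1.960) = about 88.2%
- Or, for 85% power, N = about 2,368, which is 244 fewer
- 1.1025 × 0.907 = 1.00, so the gain is about as large as the planned allowance for clustering

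A simulation of 20,000 null trials with 1,306 patients per arm at these rates, without clustering, gave a variance cut of 9.7% for the rhythm-standardised difference. Carrying the cut over to the clustered design assumes that the 1.05 factor is unchanged by adjustment.

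**4. Range over the unknown share, keeping the quoted rates.**

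| Shockable share | Implied overall survival | Variance cut | SE cut | Power at 2,612 |
|---|---|---|---|---|
| 10% | 8.4% | 5.7% | 2.9% | 87.0% |
| 17.1% | 10.0% | 7.8% | 4.0% | 87.7% |
| 20% | 10.6% | 8.3% | 4.2% | 87.9% |
| 33.8% | 13.7% | 9.3% | 4.8% | 88.2% |
| 40% | 15.1% | 9.2% | 4.7% | 88.2% |

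The power column applies each cut to the planned standard error of 0.01502. Only the 33.8% row agrees with 13.7% overall survival. At that share, if the 18.2% arm keeps the same ratio between rhythms, the cut over both arms is 11.4% and power about 89%.

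**5. The same noise seen as imbalance.** At s = 33.8% and 1,306 per arm, the standard error of the arm difference in shockable share under individual randomisation is √(2 × 0.338 × 0.662 / 1,306) = 1.9 points. An imbalance of two standard errors, 3.7 points, moves the crude difference by 3.7 × 0.222 = 0.8 points. The final boundary in Table 5 is 2.9 points. The crude standard error already includes this noise, so it is not bias; adjustment removes it.

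**6. Site and period.** The documents give no variance between sites, between periods or within clusters, so no gain can be computed for these terms.

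**The case against.** The strongest reply is that nothing here is wrong. A crude intention-to-treat difference with a cluster-robust standard error is valid, the trial was sized for it, 2,612 patients give the stated power, and the budget allows up to 3,000. That stands in full: this is a question of efficiency and robustness.

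It can also be said that to stratify, in section 15.3, means to split the results, as it does at the end of section 15.5, so that the sentence only defines the all-rhythm population. That reading is fair. It leaves the primary analysis with no covariate all the same.

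A reader might infer that the plan ignores the crossover, or that about 9% of precision is lost through rhythm, site and period together. The documents support neither. The robust variance is meant to handle within-cluster correlation and, if it is clustered on the randomised unit across its periods, it reflects the covariance that crossover creates; section 15.3 does not name the unit. The 9% is variance, it comes from rhythm alone, and it is about 5% on the scale of the standard error. Nor can one assume few clusters: section 18.2 expects more than 33 agencies, and section 13.1 allows them to be subdivided.

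Two practical objections also stand. Rhythm is recorded after cluster assignment by unblinded crews (section 13.3), so its definition must be tight. And the current version is dated July 2016 (Appendix 1), after the planned August 2015 start of execution, so the change would probably be made during accrual and would touch a monitoring plan that the DSMB approves.

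**Conclusion.** The point holds as a worthwhile improvement. Section 15.3 is valid and adequately powered as planned, but it makes no use of a strong predictor that the trial already collects, and it is silent on the site strata and the calendar periods of its own design.

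Rhythm adjustment is worth about 6% to 9% of variance, or 3% to 5% of the standard error, and about three points of power at the 33.8% share. These figures assume that the 28.4% and 6.2% rates hold at 72 hours, that the shockable share lies between 10% and 40%, and that the cluster allowance carries over. The case for site and period terms rests on the design and on protection against unequal exposure by arm. How much imbalance will occur is unknown.

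**What to change.** Before any further unblinded look, amend section 15.3 and the matching paragraph of section 3 to specify:

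- **Estimand:** the marginal risk difference in 72-hour survival over all rhythms, by intention to treat.
- **Adjustment:** initial rhythm (first recorded EMS rhythm: shockable, non-shockable, unknown), randomisation site and calendar period, by a linear model or by standardisation.
- **Variance:** cluster-robust, with the randomised cluster named as the unit.
- **Sensitivity analysis:** the crude difference as now planned.

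No new data are needed. The cost is SAP wording, slightly more analysis, and one step with the DSMB. The boundaries in Table 5 are expressed as absolute differences, so it must be confirmed how they and the information fractions apply to the adjusted estimate and its smaller standard error.

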## **15.4 Secondary Analyses**

In a similar manner, we will also study associations between the trial interventions and the secondary outcomes detailed in Section 14.2, including return of spontaneous circulation, airway management course, adverse events, hospital survival, and hospital survival with good neurologic function.

## **15.5 Subgroup Analyses**

OHCA outcomes are known to vary for different patient subsets. For example, OHCA survival is approximately 28.4% for patients with an initial “shockable” cardiac rhythms (ventricular fibrillation or tachycardia) and 6.2% for non-shockable rhythms (pulseless electrical activity and asystole). We will explore multiplicative associations between airway management strategy (ETI vs. LT) and the pertinent subgroups, including:

- Initial cardiac rhythm (shockable vs. non-shockable);
- Bystander witnessed arrest (yes vs. no);
- EMS response time (911 call to arrival on-scene: <10 vs. ≥10 mins);
- BLS unit capability of performing LT insertion (yes vs. no);
- Time of airway placement after rescuer arrival on-scene (early [<10 minutes] vs. later [≥10 minutes]);
- Use of NMB (RSI) before or during airway insertion efforts (yes vs no);
- Age (<65 vs. ≥65 years).
- Placement of advanced airway after ROSC.
- Initial airway management with non-rebreather mask only (passive ventilation).

Initial airway management with video laryngoscopy. If an [airway x subgroup] interaction is statistically significant, we will stratify the analysis by the subgroup.

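### Section 15.5 makes stratified results depend on a significant multiplicative interaction, while the trial's only stated effect measure is an absolute difference; for initial rhythm this gate can mislead in either direction

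*Combined protocol and SAP*

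**What the plan says.** Section 15.5 introduces the subgroup work with "We will explore multiplicative associations between airway management strategy (ETI vs. LT) and the pertinent subgroups" and lists ten subgroups. It closes with the rule that if an airway-by-subgroup "interaction is statistically significant, we will stratify the analysis by the subgroup". It names no model, no ratio measure, no significance level for the interaction and no effect measure for the stratified results. It does not say that subgroup estimates will be shown when the interaction is not significant.

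Section 15.3 gives the effect measure of the primary analysis: "To quantify the treatment effect, we will calculate the 95% CI for the difference in event rates". Section 15.4 treats the secondary outcomes in a similar manner. The effect sizes in Table 4 and the stopping boundaries in Table 5 are also absolute differences. Section 15.3 adds that because "randomization includes all eligible OHCA patients, we will not stratify the primary analysis by initial cardiac rhythm".

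Only one subgroup comes with survival rates. For shockable rhythms, "OHCA survival is approximately 28.4% for patients with an initial" rhythm of that kind; the contrast is "6.2% for non-shockable rhythms (pulseless electrical activity and asystole". No time point is attached to either figure.

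**The concern.** A test on a ratio scale has as its null that the odds ratio or risk ratio is the same in both levels of a subgroup. A test on the difference scale has as its null that the absolute difference is the same. When the two levels have different baseline survival, both nulls can be true only if there is no treatment effect. The two rhythm rates in 15.5 are 28.4/6.2 = 4.6-fold apart, so for any real effect the two questions part company.

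If one device is better, a ratio-scale gate could lead the report to say that the effect depends on rhythm when the trial's own measure is identical in both groups. It could also leave the rhythm-specific differences unreported when most of the absolute benefit or harm falls in one group. That second result bears on the choice of device, which Appendix 4 gives as the use of the findings. Section 16.2 also lists consistency of treatment effects across subgroups among the factors that may influence stopping.

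**Working it through.** **Inputs from the documents.** Survival 28.4% and 6.2% by rhythm (15.5). Overall baseline: "In ROC PRIMED, baseline 72-hour survival was 13.7"% (16.1). Design effect of 4.5 points (16.1: "we will use a more conservative figure of 4.5% to represent a minimal clinically significant difference"). Two-sided alpha 0.05, power 85%, 2,612 patients (1,306 per group), and up to 5% loss of precision from clustering.

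**Assumptions.** The rhythm rates are 72-hour survival. The interaction is tested at two-sided 0.05. The loss of precision is read as SE × 1.05, so variance × 1.1025. The documents give no shockable share. Solving 28.4w + 6.2(1 − w) = 13.7 gives w = 7.5/22.2 = 0.338, and 20% to 34% is used as the range.

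**Step 1: reproduce the plan's figure.** Total N = 2 × (0.137 × 0.863 + 0.182 × 0.818) × (1.960 + 1.036)² / 0.045² × 1.1025 = 2,611, against 2,612 stated. The design therefore corresponds to a rise from 13.7% to 18.2%; a fall to 9.2% would need only about 1,980.

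**Step 2: identical absolute effect in both rhythms.**
- Fall of 4.5 points (28.4 to 23.9; 6.2 to 1.7): OR 0.79 and 0.26; RR 0.84 and 0.27.
- Rise of 4.5 points (28.4 to 32.9; 6.2 to 10.7): OR 1.24 and 1.81; RR 1.16 and 1.73.

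Worked case for the OR at w = 0.338. The effective size per arm is 1,306 × 0.338/1.1025 = 400 shockable and 1,306 × 0.662/1.1025 = 784 non-shockable. The variance of the log-OR interaction is the sum of 1/[n p(1 − p)] over the four cells.
- Fall: 0.0123 + 0.0137 + 0.0219 + 0.0763 = 0.1242, SE 0.352. The log-OR difference is ln(0.792/0.262) = 1.107, z = 3.14, power Φ(3.14 − 1.96) = 88%.
- Rise: 0.0123 + 0.0113 + 0.0219 + 0.0133 = 0.0589, SE 0.243. The difference is ln(1.813/1.236) = 0.383, z = 1.58, power Φ(1.58 − 1.96) = 35%.

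**Step 3: constant ratio.** Take the ratio that moves 13.7% to 9.2% or to 18.2% and apply it in each rhythm.
- OR 0.638: differences of −8.2 and −2.2 points (3.8-fold).
- OR 1.402: +7.3 and +2.3 points (3.2-fold).
- RR 0.672 or 1.328: 9.3 and 2.0 points either way (4.6-fold).

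**Step 4: simulated rejection rates.** Wald interaction tests, N = 2,612, shockable share 20% to 34%, 200,000 trials per scenario.

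| Truth | OR test | RR test | Risk-difference test |
|---|---|---|---|
| No effect | 5% | 5% | 5% |
| −4.5 points in both | 90–91% | 95–96% | 5% |
| +4.5 points in both | 31–35% | 48–50% | 5% |
| Constant OR, fall | 5% | 6% | 32–47% |
| Constant OR, rise | 5% | 7% | 21–30% |
| Constant RR, fall | 6% | 5% | 45–63% |
| Constant RR, rise | 7–8% | 5% | 38–54% |

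With the 88% from the normal approximation in step 2, the fall is quoted as 88% to 96%.

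**Sensitivity.** At 3,000 patients and shares of 25% to 34%, the equal-effect rates are 37–55% (rise) and 94–98% (fall). For an equal effect of 2.9 points, the final boundary in Table 5, a normal approximation with variance × 1.05 and shares of 20% to 40% gives 19–29% (rise) and 40–54% (fall).

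**The case against.** The text is thinner than the concern would like. Multiplicative may mean no more than a product term, which can sit in an identity-link model, and no odds ratio, risk ratio or log link is named. Section 15.5 also does not say that the stratified results would be risk differences; that is carried over from 15.3 and 15.4. Both points stand. They narrow the finding to a scale and model that are unspecified and, on the natural reading, not aligned with the trial's measure.

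A reader might infer that the gate always fires when the absolute effect is uniform. It does not: for a rise, the direction that reproduces 2,612, it fires half the time or less. The high figure needs a fall that takes non-shockable survival from 6.2% to 1.7%. That is, however, the direction of the 13.7% (ETI) against 8.7% (SGA) contrast in 16.1, and the trial tests for superiority either way.

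Nor is the 5% rejection under a constant ratio an error of the test: its null is then true, and ratio interactions are a legitimate convention. A constant ratio also lets a reader recover the absolute effects from the baseline rates. What remains is that the stated rule provides for no stratified results in that case, and the absolute effects by rhythm would have to be reconstructed.

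Finally, the subgroup work is exploratory, and nothing in 16.2 or 22.2 ties the monitoring board to this gate. That limits the weight of the point.

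**Conclusion.** The point holds in limited form. If the interaction is tested on a ratio scale, the gate for initial rhythm would trigger about 31% to 50% of the time (rise) or 88% to 96% (fall) under an identical 4.5-point effect. It would trigger about 5% of the time under a constant OR or RR, although the absolute effects differ about 3- to 4.6-fold. This rests on treating 28.4% and 6.2% as 72-hour survival, on an assumed shockable share, and on an interaction level of 0.05.

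Two broader readings are not supported. The primary conclusion is not at risk: 15.3 keeps the primary analysis unstratified by rhythm, and its test, CI and sample size do not depend on 15.5. Nor can the rule be shown to fail for every subgroup. Only rhythm has stated rates, and where baselines are similar the scales nearly agree. This is a cheap improvement to an exploratory analysis.

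**What to change.** In 15.5:
- Remove the significance gate. State that the risk difference and its 95% CI, with the same cluster-robust standard error as 15.3, will be reported in each level of every baseline subgroup whatever the interaction p-value.
- Name the interaction model and significance level. Report the interaction on the risk-difference scale (for example, an identity-link model) alongside a ratio-scale interaction whose measure is named.

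The first change does most of the work: once every level is shown, the scale of the test matters much less. Replacing the ratio test outright would be partly a matter of preference, and ratios may carry over better to populations with other baseline survival, so both are kept.

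The cost is two or three sentences and a slightly longer exploratory table, with no new data or patients. The risk-difference interaction test has limited power of its own: about 24% to 63% in the constant-ratio scenarios at shares of 25% to 34%, and as low as 21% at a 20% share. A non-significant result should therefore not be read as evidence of a uniform effect.

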### 12.3.1 LT Device and Technique

The LT is a novel airway device that is inserted blindly through the mouth. The device is designed so that the distal end sits in the proximal esophagus. A single port results in inflation of proximal (hypopharyngeal) and distal (esophageal) cuffs. Fenestrations between the cuffs allow insufflated air and oxygen to indirectly enter the tracheal. (Figure 8)

King Systems is the manufacturer and distributor of LT airways in the United States. There are several such models, including reusable (autoclavable) models as well as models with an esophageal port. We expect that EMS agencies will use only the disposable models of the King LT (LT-D and LTS-D).

Use of the LT in adults with OHCA has been described in a range of studies.

[figure not shown]

Figure 8 – Examples of Laryngeal Tube

[http://www.ambuusa.com/usa/products/clinical\\_studies/king\\_lt%E2%84%A2.aspx](http://www.ambuusa.com/usa/products/clinical_studies/king_lt%E2%84%A2.aspx)

<http://theopsdeck.com/MEDKIT%20CONTENTS/PROD%20-%20AWY.King%20LTD.PMI.htm>

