#### **12.5.4 Use of Neuromuscular Blocking Agents**

The use of neuromuscular blocking (NMB) agents to facilitate ETI is termed “Rapid Sequence Intubation” (RSI). Most OHCA patients are flaccid and do not require RSI. On rare occasion, an OHCA patient may develop trismus, requiring the use of RSI. RSI is technique reserved for a very small subset of specially trained paramedics. Of the ground EMS agencies in ROC that will participate in the trial, few use RSI. Also, an air medical crew capable of performing RSI may be present on scene of an OHCA.

Subjects receiving NMB (RSI) prior to (or during) ETI or LT insertion efforts will be examined in separate subgroup analyses.

Subjects receiving NMB agents after successful airway insertion will not be examined separately.

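### Five of the ten planned subgroups are set by care given after assignment, so their arm comparisons cannot be read as treatment effects and one interaction cannot usefully be estimated

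*Combined protocol and SAP*

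**What the plan says.** Section 15.5 introduces its subgroups as an exploration, on the multiplicative scale, of airway strategy by subgroup. Ten items follow. Nine are bulleted; the tenth, video laryngoscopy, runs into the closing rule: "Initial airway management with video laryngoscopy. If an [airway x subgroup] interaction is statistically significant, we will stratify the analysis by the subgroup". The section gives no significance level for the interactions and no multiplicity handling. It does not separate baseline factors from factors that arise during care.

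Other sections bear on this:

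- Section 13.1: when several participating agencies attend, the first arriving unit determines the assignment.
- Sections 12.2 and 12.3: basic-level crews are limited to bag-valve-mask in the ETI arm, but may place the LT in the LT arm if trained to do so. Section 12.4 leaves airway timing open.
- Section 12.2.2 allows video laryngoscopy for the first intubation attempt. Section 12.3.1 says of the other device: "The LT is a novel airway device that is inserted blindly through the mouth".
- Section 12.5.4 opens with "The use of neuromuscular blocking (NMB) agents to facilitate ETI is termed" rapid sequence intubation, and commits to separate subgroup analyses of patients who receive these agents before or during ETI or LT insertion.
- Section 3 (Outcomes) and Section 14.2.2 make insertion time part of a secondary outcome.
- Section 9 enrols patients who receive only bag-valve-mask or non-rebreather support.

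**The concern.** Randomization makes the arms comparable within a subgroup only if assignment cannot influence membership. For a factor such as initial rhythm that is reasonable. For a factor determined by how the airway was managed it is not: the ETI patients placed early and the LT patients placed early may be different kinds of patient. A difference between them then mixes any treatment effect with a difference in case mix, and the data cannot separate the two.

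At stake are the secondary messages of the trial, such as whether one strategy looks better when the airway goes in early or after pulses return. Subgroup results also go beyond exploratory tables. Section 16.2 names consistency across subgroups among the factors that may influence stopping, and Section 22.2 has the DSMB monitor the a priori subgroups.

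**Working it through.** Section 15.5 states no calculated figure, so there is none to reproduce. The check has four steps.

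**1. Classify the ten items by when they are settled.**

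Baseline (five): initial rhythm, bystander-witnessed status, EMS response time, LT capability of the basic-level unit, age.

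Settled by care after assignment (five):

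| Item | Problem, from the documents |
|---|---|
| Time of airway placement | Itself an outcome (Sections 3, 14.2.2); assignment can shift it (12.2 vs 12.3); undefined for enrolled patients with no advanced airway (9) |
| Neuromuscular blockade | Described as an aid to ETI (12.5.4) |
| "Placement of advanced airway after ROSC" | Depends on the course of resuscitation and on airway timing; undefined without an advanced airway |
| Non-rebreather mask only | Recorded after assignment; depends partly on local protocol (3, 9) |
| Initial video laryngoscopy | An intubation technique (12.2.2); the LT goes in blindly (12.3.1) |

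For the last item the LT cell is empty under protocol-adherent care. Video laryngoscopy could appear there only as rescue, which is not initial management, or as a deviation.

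**2. Show that a subgroup difference can arise with no effect.** All inputs here are assumptions, except that overall survival is set to the 13.7% baseline in Section 16.1. Suppose 40% of patients are always placed early (survival 20%), 15% are placed late under ETI but early under LT (14%), and 45% are always placed late (8%). Airway strategy changes nobody's survival.

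- Overall, each arm: 0.40×20 + 0.15×14 + 0.45×8 = 8.0 + 2.1 + 3.6 = 13.7%.
- Early: ETI 20.0%; LT (8.0 + 2.1)/0.55 = 18.4%. Difference −1.6 points.
- Late: ETI (2.1 + 3.6)/0.60 = 9.5%; LT 8.0%. Difference −1.5 points.

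Now swap the prognosis, so that always-early patients survive at 8% and always-late at 20% (overall 3.2 + 2.1 + 9.0 = 14.3% in both arms).

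- Early: ETI 8.0%; LT (3.2 + 2.1)/0.55 = 9.6%. Difference +1.6.
- Late: ETI (2.1 + 9.0)/0.60 = 18.5%; LT 20.0%. Difference +1.5.

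Returning to the first set and changing only the movers' survival from 14% to 20% gives an early difference of 11.0/0.55 − 20.0 = 0 and a late difference of 8.0 − (3.0 + 3.6)/0.60 = −3.0. With no movers, every difference is zero.

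**3. Ask whether this bias would fire the stratify rule.** In the first set the odds ratios (LT vs ETI) are (0.184/0.816)/(0.20/0.80) = 0.90 early and (0.08/0.92)/(0.095/0.905) = 0.83 late. Their ratio is 1.09.

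- With 1,306 per arm and clustering ignored, survivors/total are 104.5/522.4 (ETI early), 74.4/783.6 (ETI late), 131.9/718.3 (LT early) and 47.0/587.7 (LT late).
- The standard error of the log ratio is the root of the summed reciprocals of the eight survivor and death counts, 0.243.
- So z = 0.083/0.243 = 0.34, and a two-sided 0.05 test is significant about 6% of the time, close to its nominal rate.

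The bias sits within the strata and hardly shows as an interaction.

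**4. Multiplicity, as a secondary note.** Assume independent tests, each at 0.05; the plan states neither. The chance of at least one false interaction is 1 − 0.95^k: 37% for the nine estimable tests and 23% for the five baseline tests.

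**The case against.** The strongest reply is that nothing important depends on these subgroups. Section 15.3 fixes the primary analysis as intention-to-treat on overall 72-hour survival and declines to stratify it by rhythm. Section 16.2 says how the primary estimate, interval and p-value will be reported. Section 15.5 only explores, and stratifying after a significant interaction most naturally means giving stratum estimates. This stands. A reader might infer that a significant interaction lets a subgroup result replace the primary one; no passage says so.

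A reader might also infer that the bias would trigger the rule. Step 3 shows that in the example it would rarely do so. Nor does the example show that LT would be disadvantaged, or by how much: its inputs are assumed and the sign reverses. It also gives everyone an advanced airway, which Section 9 does not require.

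The five items are not equally exposed. Non-rebreather use is partly an agency characteristic. Section 12.5.4 calls the need for rapid sequence intubation rare, so sparse data may be the larger problem there. ROSC before airway placement is not the trial's ROSC outcome, which Section 14.2.1 defines at ED arrival. These points change the degree of exposure, but all five items are still settled after assignment.

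Finally, counting all ten tests would give 40% in step 4, but that includes the interaction that cannot usefully be estimated. Correlation between tests would probably lower the figures.

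**Conclusion.** The point holds for the subgroup analyses. Five of ten planned interactions condition on care given after assignment, and one of them has no usable comparison. Differences between arms inside these subgroups can appear without any treatment effect. The 1.5-point figure is an illustration that this can happen and should not be read as an estimate: size and direction depend on shifts that the documents do not give, and the bias vanishes if assignment moves nobody between subgroups. The documents do not support the stronger conclusion that the primary intention-to-treat result or its type I error is compromised.

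The count of ten treats video laryngoscopy as a list item, which is how the text reads. The list is not worded as exhaustive.

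**What to change.** - In Section 15.5, limit interaction tests to the five baseline factors: initial rhythm, witnessed status, EMS response time, LT capability of the basic-level unit, and age.
- Report the other five descriptively by arm, without arm-effect tests, and video laryngoscopy within the ETI arm only.
- Align Section 12.5.4, which separately promises subgroup analyses for neuromuscular blockade. Editing 15.5 alone would leave the two sections in conflict.
- Replace the last sentence of 15.5 with a statement that the overall intention-to-treat result stands and that stratum estimates, with 95% confidence intervals, are exploratory.
- State the interaction significance level. Adjustment for five tests, for example by Holm, is optional for exploratory work.

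The cost is five exploratory contrasts lost as comparative results. Data collection, sample size and clinical procedures do not change. Keeping LT capability of the basic-level unit preserves a baseline factor related to early placement.
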